2.4.7 Analyses of anti-alirocumab antibodies variables

The summary of ADA variables will be presented on the ADA population, taking into account all samples regardless of timing in relation to injections but within each study period separately.

Within each dosing regimen cohort, the double-blind period will be presented by treatment group, as well as, according to baseline body weight (as per IVRS/IWRS stratum) and by up-titration / dose-adjustment status.

The OL period will be presented also within each dosing regimen cohort, according to the treatment received in the double-blind period (placebo or alirocumab) and overall.

All summaries described below will be presented for each study period respectively.

ADA results (negative or positive) by time point;

- Neutralizing status (negative or positive) by time point for positive ADA;
- ADA titers using descriptive statistics (median, minimum and maximum) for positive ADA by time point;
- Number (%) of patients with pre-existing ADA and number (%) of patients with treatmentemergent ADA positive response;
- Number (%) of patients with persistent/indeterminate/transient treatment-emergent ADA positive response;
- Time to onset of treatment-emergent ADA positive response using descriptive statistics, beginning from the first IMP administration within the relevant period (double-blind or OL).
- Number (%) of patients with at least one neutralizing ADA.

If appropriate, correlations between ADA parameters (eg, titers, treatment-emergent ADA positive status, neutralizing status) and PK, safety and/or efficacy endpoints will be also explored (eg, scatter plot, summary of TEAEs for ADA positive patients).

In addition, the following summaries will be also presented on ADA population according to previous participation in the DFI14223 study:

- Number (%) of patients with pre-existing ADA and number (%) of patients with treatmentemergent ADA positive response;
- Number (%) of patients with persistent/indeterminate/transient treatment-emergent ADA positive response.

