5.3 OTHER

- To evaluate the development of anti-alirocumab antibodies after 80 weeks of open label treatment.
- To evaluate the pharmacokinetics (PK) of alirocumab.

Amended Clinical Trial Protocol 03 EFC14643 - alirocumab 06-Jan-2021 Version number: 1

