2 STATISTICAL AND ANALYTICAL PROCEDURES

2.1 ANALYSIS ENDPOINTS

2.1.1 Demographic and baseline characteristics

The baseline value is defined as the last available value obtained before or equal to the date and time of the first double-blind Investigational Medicinal Product (IMP) injection in the EFC14643 study. In case of missing time of the first double-blind IMP injection and/or time of assessment, the baseline value is defined as the last available value obtained before or equal to the date of the first double-blind IMP injection.

For patients randomized and not treated, the baseline value is defined as the last available value obtained before or equal to the date and time of randomization. In case of missing time of assessment, the baseline value is defined as the last available value obtained before or equal to the date of the randomization.

All baseline safety and efficacy parameters are presented along with the summary statistics in the safety and efficacy sections (Section 2.4.4 and Section 2.4.5).

Demographic characteristics

Demographic variables include:

- Gender (Male, Female).
- Age in years (quantitative and categorical variable: <12 and ≥ 12 to <18 years, as well as $<10, \ge 10$ to <12, and ≥ 12 to <18 years).
- Race (White, Black or African American, Asian, American Indian or Alaska Native, Native Hawaiian or other Pacific Island, other).
- Ethnicity (Hispanic or Latino, Not Hispanic or Latino).
- Weight in kilograms (quantitative and categorical variable: <50 and ≥ 50 kg).
- Height in centimeters (quantitative variable).
- Body mass index (BMI) in kg/m² (quantitative and categorical variable: <P5: Underweight, ≥P5 to <P85: Healthy weight, ≥P85 to <P95: Overweight and ≥P95: Obesity, using the World Health Organization [WHO] growth reference 5-19 years (1, 2, 3).

Medical or surgical history

Medical or surgical history includes medical history of specific interest such as cardiovascular (CV) history and cardiovascular risk factors, subject medical allergic history and family medical allergic history, and relevant medical or surgical history other than hypercholesterolemia, CV/CV

Risk and allergies. Medical and surgical history will be described using all pre-printed terms collected in the dedicated medical history e-CRF pages.

CV history and CV Risk factors history will be based on items pre-listed in the dedicated medical history e-CRF page and include:

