2.1.6 Anti-alirocumab antibodies variables

Anti-alirocumab antibodies (ADA) are assessed:

- During the double-blind period at Visit 4 (Week 0/Day 1, before the first IMP injection), at Visit 6 (Week 12) and Visit 7 (Week 24)/or early termination for patients not proceeding into OL period.
- During the OL period at Visit 11 (Week 68) and Visit 14 (Week 104) /or early termination for patients proceeding into OL period.

ADA measurements will be assigned to the same analysis windows as defined for efficacy endpoints (Table 5 and Table 6). The following variables will be described for both double-blind and open-label periods:

• ADA response (Positive or Negative).

For ADA positive:

- Titer levels.
- Neutralizing status (Positive or Negative).
- Pre-existing positive ADA defined as patients with positive ADA response at baseline with less than 4-fold increase in titer in the post-baseline period.
- Treatment-emergent positive ADA response defined as:
 - Patients with no ADA positive response at baseline but with any positive response in the post-baseline period (for double-blind period: up to Visit 7 (Week 24)/ early termination visit for patients not proceeding into open-label period or first open-label IMP injection for patient proceeding into open-label period, for open-label period: up to Visit 14 (week 104)/early termination.

OR

- Patients with a positive ADA response at baseline and at least a 4-fold increase in titer in the post-baseline period (for double-blind period: up to Visit 7 (Week 24)/early termination for patients not proceeding into OL period or first open-label IMP injection for patient proceeding into OL period, for OL period: up to Visit 14 (week 104)/early termination.

For treatment-emergent positive ADA, the following categories for ADA duration will be applied:

- A persistent positive response is a treatment-emergent ADA positive response detected in at least 2 consecutive post-baseline samples separated by at least a 12-week period.
- An indeterminate duration positive response is defined as ADA present only at the last sampling time point.
- A transient positive response is defined as any treatment-emergent positive ADA response that is neither considered persistent nor indeterminate.

In addition, potential ADA samples to be collected for patients who do not enter into OL period or who prematurely discontinue the double-blind period and have a titer \geq 240 at their end of treatment visit will be listed.

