2.3.3 Anti-alirocumab antibody population

The ADA analysis will be performed on all randomized and treated patients (safety population) with an available ADA sample at Week 0 (baseline) and at least one non-missing ADA sample post first double-blind IMP injection and up to Week 24/early termination or up to first open-label IMP injection for patient proceeding into open-label period.

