2.4.5 Analyses of safety data

No formal inferential testing will be performed for either study period. Summaries will be descriptive in nature. All summaries of safety results described below will be presented for each study period respectively, unless otherwise noted.

General common rules

All safety analyses will be performed on the safety population for the double-blind period and on the OL population for the OL period, as defined in Section 2.3.2 unless otherwise specified, using the following common rules:

- Safety data in patients who do not belong to the safety population (ie, exposed but not randomized) will be listed separately.
- The baseline value for both double-blind and OL periods is defined as the last available value obtained up to the date and time of the first double-blind IMP injection in EFC14643 study, except otherwise specified.
- PCSA values are defined as abnormal values considered medically important by the Sponsor according to predefined criteria/thresholds based on literature review and defined by the Sponsor for clinical laboratory tests and vital signs, PCSA in children [Appendix A] and PCSA in adults version dated May 2014 [Appendix B]). Considering that the threshold defined in the PCSA list for monocytes and basophils can be below the ULN, the following PCSA criteria will be used for the PCSA analysis of monocytes and basophils:
 - PCSA criterion for monocytes: >0.7 Giga/L or > ULN (if ULN ≥ 0.7 Giga/L)
 - PCSA criterion for basophils: >0.1 Giga/L or > ULN (if ULN \ge 0.1 Giga/L)
- PCSA criteria will determine which patients had at least 1 PCSA during the TEAE period, taking into account all evaluations performed during the TEAE period, including nonscheduled or repeated evaluations.
- The treatment-emergent PCSA denominator by group for a given parameter will be based on the number of patients assessed for that given parameter at least once during the TEAE period.
- All measurements, scheduled or unscheduled, fasting or not fasting, will be assigned to analysis windows defined in Section 2.5.4, Table 5 and Table 6 in order to provide an assessment for Week 4 to Week 104 time points.

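### Open-label ADA tables report antibodies that arose in the double-blind period as open-label treatment-emergent responses, with onset timed from the first open-label injection

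*SAP*

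**What the plan says.** **Baseline.** SAP 2.1.1 ties baseline to the start of double-blind dosing: "The baseline value is defined as the last available value obtained before or equal to the date and time of the first double-blind". For safety data, SAP 2.4.5 applies the same starting point to open label, unless otherwise specified: "The baseline value for both double-blind and OL periods is defined as the last available value obtained up to the date and time". The ADA sections specify nothing else. The ADA population in SAP 2.3.3 requires patients "with an available ADA sample at Week 0 (baseline").

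**Treatment-emergent response.** SAP 2.1.6 counts "Patients with no ADA positive response at baseline but with any positive response in the post-baseline period", or a rise in titre of at least 4-fold for patients already positive at baseline. For the open-label period it gives only where the period ends: "for open-label period: up to Visit 14 (week 104)/early termination". It names no new reference sample and does not exclude patients who were already treatment-emergent.

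**Sampling.** Double-blind samples are taken at Week 0 and then "at Visit 6 (Week 12) and Visit 7 (Week 24"). Scheduled open-label samples are at Weeks 68 and 104 only. Protocol 9.3.2.1 has all scheduled samples drawn before the injection, so the Week 24 sample precedes the first open-label dose.

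**Summaries.** SAP 2.4.7 uses samples within each period separately and repeats all ADA summaries for each period, including "Time to onset of treatment-emergent ADA positive response using descriptive statistics, beginning from the first IMP administration within the relevant period". Open-label results are shown within each dosing regimen cohort, by double-blind treatment and overall.

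**Objective.** Protocol 5.3 (Other): "To evaluate the development of anti-alirocumab antibodies after 80 weeks of open label treatment".

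**The concern.** Patients given alirocumab in the double-blind period start open label with 24 weeks of exposure behind them. Under these rules their open-label status is derived afresh against a sample taken before any of that exposure, while the onset clock starts after it. A response that appeared at Week 12 or 24 and is merely detected again later is then listed as an open-label treatment-emergent response, dated from the wrong injection.

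The former-alirocumab and overall columns would mix old responses with new ones, and the onset statistics in those columns would place early antibodies late. Someone using these tables to judge when antibodies arise could be misled about late immunogenicity.

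Former placebo patients raise a smaller problem in the other direction. One who is first positive at the predose Week 24 sample, before receiving alirocumab in this study, and who stays positive is counted as emergent on open-label alirocumab.

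**Working it through.** **1. Reproduce the plan's own days.** SAP Table 6 counts open-label days from the first open-label injection (Day 1). The target day should be (week − 24) × 7 + 1.
- Week 68: 44 × 7 + 1 = 309, as in Table 6.
- Week 104: 80 × 7 + 1 = 561, as in Table 6.

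**2. Onset the open-label table would show.** Weeks since first open-label injection = (day − 1)/7.
- Week 68: (309 − 1)/7 = 44.0 weeks. The window of Days 288 to 329 gives 41.0 to 46.9 weeks.
- Week 104: (561 − 1)/7 = 80.0 weeks. The window of Days 540 to 581 gives 77.0 to 82.9 weeks.
- Early-termination or unscheduled samples would give other values.

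**3. A worked patient.** Take a patient on double-blind alirocumab, negative at Week 0 and positive at Weeks 24 and 68.
- Double-blind table: treatment-emergent, onset about 24 weeks.
- Open-label table: treatment-emergent, onset about 44 weeks.
- One clock from first study alirocumab: a single response, onset about 24 weeks.

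**4. How general this is.** For a patient negative at Week 0, list all positive/negative patterns at Weeks 12, 24, 68 and 104.
- 12 of the 16 patterns are treatment-emergent in the double-blind period.
- 9 of those 12 appear again as open-label responses: 6 at about 44 weeks (positive at Week 68) and 3 at about 80 weeks (positive at Week 104 only).
- Against a Week 24 reference, only 3 of the 9 (positive at Week 12, negative at Week 24) would count as new without a 4-fold titre rise.

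These are counts of patterns, not probabilities.

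**5. Duration classes.** SAP 2.1.6 calls a response persistent if it is found in at least two consecutive post-baseline samples at least 12 weeks apart. Take a patient negative at Week 12, positive at Weeks 24 and 68, and negative at Week 104. Read within each period, this is indeterminate in double-blind (positive only at the last sample) and transient in open label. Read across periods, the two consecutive positives are 68 − 24 = 44 weeks apart, which meets the persistent definition.

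**6. Size.** The documents give no ADA rate, so 3–8% is an assumption. It stands for the share of alirocumab patients who become positive in the double-blind period and are detected again in open label. Planned enrolment is 50 alirocumab patients per cohort (Protocol 11.1), and Protocol 11.4.4 excludes ADA from pooling across cohorts.
- Lower end: 0.03 × 50 = 1.5 patients per cohort.
- Upper end: 0.08 × 50 = 4 patients per cohort.

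Discontinuations before open label would lower both.

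**The case against.** The strongest reply is that Week 0 is a legitimate reference. The objective asks about antibodies after 80 weeks of open-label treatment, and status against an untreated baseline answers that. The SAP uses the same baseline for efficacy and safety in both periods, and moving it to Week 24 would give former-alirocumab patients an on-drug baseline. This stands for incidence, provided carried-over responses can be told apart from new ones. It does not rescue the onset time, which pairs a pre-exposure reference with a clock that starts 24 weeks into exposure. Nor does reading the post-baseline period cumulatively help: onset of a double-blind response measured from the first open-label injection would then be negative.

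Several safeguards also stand. Open-label results are split by double-blind treatment, and for former placebo patients new to alirocumab the open-label clock is right. Results and titres by time point appear in both periods, so a careful reader can set Weeks 12 and 24 beside Weeks 68 and 104. Onset is coarse in any case: a truly new response found at a scheduled open-label visit is also dated at about 44 or 80 weeks.

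A reader might infer that patients are counted twice in one total, or that carried-over cases should be reckoned against all 100 or so alirocumab patients. The documents do not support either. No ADA count combining the periods is planned, and each row is confined to one cohort.

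**Conclusion.** The point holds for the former-alirocumab and overall columns of the open-label ADA tables. There, a double-blind response that is detected again is reported as open-label treatment-emergent, with onset of about 44 or 80 weeks where the first study exposure puts it at about 12 or 24. The Week 24 placebo case is a lesser instance of the same gap. The conclusion rests on reading the Week 0 baseline into the open-label rule, which follows from SAP 2.1.1 and 2.3.3 because SAP 2.1.6 says only baseline. It does not depend on any particular ADA rate; only the estimate of 1.5–4 patients per cohort row does.

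It would be tempting to conclude that the open-label incidence is simply wrong, or that the trial's immunogenicity findings are compromised. That goes too far. The Week 0 reference is defensible if carried-over cases are shown separately. The secondary ADA objective concerns the double-blind period, where incidence and onset are unaffected. All ADA analyses are descriptive, so the primary result and the type I error are untouched.

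**What to change.** Amend SAP 2.1.6 and 2.4.7 before the open-label ADA tables are produced:

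- **Split open-label treatment-emergent responses into two lines.** Carried over: already positive or treatment-emergent before the first open-label injection. New in open label: negative at the last sample before the first open-label injection, or at least a 4-fold titre rise from it. Some patients meet both descriptions, such as those positive at Week 12 and negative at Week 24, or those with a boosted titre. The SAP should say which line takes them or give them their own.
- **Time onset from the first alirocumab injection in this study.** This is the first double-blind injection for the alirocumab group and the first open-label injection for the placebo group. A placebo patient already positive at Week 24 goes on the carried-over line and gets no onset time unless the response also qualifies as new.
- **Classify persistent, indeterminate and transient responses across consecutive samples from both periods** for double-blind alirocumab patients.
- **Keep the planned display by previous DFI14223 participation.** Those patients may have received alirocumab before Week 0, so the first injection in this study need not be their first exposure.

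The cost is SAP wording and a few derived variables. No new sample is needed, because the predose Week 24 sample is already scheduled.

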2.4.8 Analyses of pharmacokinetic and pharmacodynamic variables

Within each dosing regimen cohort, concentrations of total alirocumab in serum (C_{trough}), free and total PCSK9 concentrations will be summarized on the PK population by treatment group and up-titration/dose-adjustment status using descriptive statistics. These summaries will be also provided by baseline BW (as per IVRS/IWRS) in the treatment groups.

Time profiles for C_{trough} concentration, total and free PCSK9 will be also provided by group using graphs (mean \pm SE or Median, as appropriate).

Additional plots will be prepared, as deemed necessary (eg, to explore the relationship with some safety or efficacy endpoints of interest).

Concentrations of total alirocumab in serum as well as concentrations of free and total PCSK9 might be used for population PK modeling if considered necessary and the results of population PK modeling will be reported separately from the study report.

2.4.9 Analyses of quality of life variables

Not applicable.

2.5 DATA HANDLING CONVENTIONS

2.5.1 General conventions

The following formulas will be used for computation of parameters:

Time from diagnosis of heFH

Time from diagnosis (years) = (Date of informed consent – Date of diagnosis*) / 365.25.

(*): In case the month of diagnosis would be missing, it will be put equal to 1st JANUARY if the year of diagnosis equals the year of informed consent; it will be put equal to 1st JUNE otherwise. In case only the day of diagnosis would be missing, it will be put equal to the 1st of the month.

Date of last dose of IMP (for double-blind and for open-Label)

The date of the last injection in the double-blind period is equal to the last date of administration reported on injection administration case report form page in double-blind period or missing if the last administration date is unknown.

The date of the last injection in the open-label period is equal to the last date of administration reported on injection administration case report form page in open-label period or missing if the last administration date is unknown.

Renal function formulas

Creatinine clearance value will be derived using the modified Schwartz equation presented in Appendix H.

Lipids variables, laboratory safety variables, Hs-CRP

For data below the lower limit of quantification (LLOQ) / limit of linearity, half of the lower limit value (ie, LLOQ/2) will be used for quantitative analyses. For data above the upper limit of quantification (ULOQ) / limit of linearity, the upper limit value (ie, ULOQ) will be used for quantitative analyses.

The above rules will not be applied for the calculated LDL-C and non-HDL-C when HDL-C value is below the LLOQ. The value of LLOQ/2 for HDL-C will be used to obtain the non-HDL-C and calculated LDL-C used for quantitative analyses.

Below is an example of data for a "dummy" patient, with the values that will be used in quantitative analyses for each parameter.

Parameter	Value recorded in the database	Value used in the analysis
TC	255 mg/dL	255 mg/dL
HDL-C	<10 mg/dL	5 mg/dL
Calculated LDL-C ^a	<221 mg/dL	216 mg/dL
NON-HDL-C	<255 mg/dL	250 mg/dL
TG	172 mg/dL	172 mg/dL

Table 4 - Example of lipid data for a "dummy" patient

a Friedewald formula for calculated LDL-C (when lipid expressed in mg/dL: LDL-C=NON-HDL-C-0.2*TG)

Pharmacokinetic variables

Data below the LLOQ are set to zero.

2.5.2 Data handling conventions for secondary efficacy variables

See Section 2.1.3.2.

2.5.3 Missing data

For categorical variables, patients with missing data are not included in calculations of percentages unless otherwise specified. When relevant, the number of patients with missing data is presented.

Handling of baseline definition if time of first double-blind administration or time of assessment at Week 0 visit is missing

If the time of the first double-blind administration or the time of assessment at Week 0 visit is missing, then the baseline value is defined as the last available value obtained before or on the day of the first double-blind IMP administration

Handling of computation of treatment duration and compliance if investigational medicinal product first or end of treatment date is missing

If the last or first injection date is missing, the exposure duration and compliance will be left as missing.

Handling of safety and efficacy analysis periods and survival analysis if investigational medicinal product end of treatment date is missing

If the last injection date of double-blind period or open-label period is missing, then this date is imputed to the earliest between:

- the last day of the month and year, when applicable or else the 31st of December of the year,
- the date of the end of treatment visit of the period (Double-blind period: Week 24 visit for patients who completed the double-blind study treatment period as per protocol, early end of treatment visit for patients who prematurely discontinued the IMP; open-label period: Week 104 for patients who completed the open-label study treatment period as per protocol, early end of treatment visit for patients who prematurely discontinued the IMP; open-label period: Week 104 for patients who completed the open-label study treatment period as per protocol, early end of treatment visit for patients who prematurely discontinued the IMP),
- and the date of the last contact,

for the purpose of safety and efficacy analysis period start and/or end.

Handling of medication missing/partial dates

No imputation of medication start/end dates or times will be performed. If a medication date or time is missing or partially missing and it cannot be determined whether it was taken prior or concomitantly, it will be considered a prior, concomitant, and post-treatment medication.

Handling of adverse events with missing or partial date/time of onset

Missing or partial AE dates and times will be imputed so that if the partial AE date/time information does not indicate that the AE started prior to treatment or after the TEAE period, the AE will be classified as treatment emergent. These data imputations are for categorization purpose only and will not be used in listings. No imputation is planned for date/time of AE resolution.

Handling of adverse events when date and time of first investigational medicinal product administration is missing

When the date and time of the first IMP administration is missing, all AEs that occurred on or after the day of randomization will be considered as TEAEs.

When the time of the first double-blind IMP administration is missing, all AEs that occurred on the day of the first double-blind IMP administration will be considered as treatment-emergent AEs.

Handling of missing assessment of relationship of adverse events to investigational medicinal product

If the assessment of the relationship to IMP is missing, then the relationship to IMP has to be assumed and the adverse event considered as such in the frequency tables of possibly related adverse events, but no imputation should be done at the data level.

Handling of missing severity of adverse events

If the severity is missing for 1 of the treatment-emergent occurrences of an AE, the maximal severity on the remaining occurrences will be considered. If the severity is missing for all the occurrences, a "missing" category will be added in the summary table.

Handling of potentially clinically significant abnormalities

If a patient has a missing baseline he will be grouped in the category "normal/missing at baseline."

For PCSAs with 2 conditions, one based on a change from baseline value or a normal range and the other on a threshold value, with the first condition being missing, the PCSA will be based only on the second condition.

For a PCSA defined on a threshold and/or a normal range, this PCSA will be derived using this threshold if the normal range is missing; eg, for eosinophils the PCSA is >0.5 GIGA/L or >ULN if ULN \geq 0.5 GIGA/L. When ULN is missing, the value 0.5 should be used.

Measurements flagged as invalid by the laboratory will not be summarized or taken into account in the computation of PCSA values.

